3.5 Endpoints

3.5.1 Primary Endpoint

The primary endpoint is the comparison of inpatient psychiatric hospitalization rates (proportion of subjects with ≥ 1 inpatient psychiatric hospitalization) between the retrospective period (Month 1 to 3) while subjects are on oral standard-of-care antipsychotic treatment and the prospective period (Month 1 to 3) after the subjects switch to Abilify MyCite.

3.5.2 Secondary Endpoint

Improved adherence based on overall PDC with Abilify MyCite versus retrospective oral atypical antipsychotics.

3.5.3 Exploratory Endpoints

[REDACTED]

[REDACTED]

[REDACTED]

[REDACTED]

[REDACTED]

[REDACTED]

[REDACTED]

Protocol 031-201-00301

[REDACTED]

3.5.4 Safety Endpoints

Adverse events will be examined by frequency, severity, seriousness, and discontinuation (all cause and due to AEs). The safety and tolerability of Abilify MyCite, as assessed by the frequency and severity of SAEs, device-related nonserious AEs, potential hepatotoxicity cases, and pregnancies will be assessed along with an evaluation of any product quality complaints that arise. The Columbia Suicide Severity Rating Scale (C-SSRS) will be completed at baseline and all subsequent visits to assess the risk of suicide events and to classify reported suicide events.

3.6 Measures to Minimize/Avoid Bias

This trial is open-label.

3.7 Trial Procedures

The duration of this trial from first subject enrolled to first subject completed is estimated to be up to approximately 8.5 months including a 45-day screening period and a 6-month prospective phase that includes a required 3 months (Months 1 to 3) of Abilify MyCite

Protocol 031-201-00301

treatment. This will be followed, at investigator discretion, to either change to standard-of-care antipsychotic treatment (eg, oral or LAI) or remain on Abilify MyCite for the second 3-month period (Months 4 to 6), during the prospective phase. The final trial visit will be on Month 6/ET and will be followed by a 30-day (\pm 3 day) safety follow-up period for subjects continuing on Abilify MyCite. For subjects completing Months 4 to 6 on standard of care, a 30-day safety follow-up period is not required. Total length of participation in the trial will vary depending on the screening duration and if the subjects remain on Abilify MyCite treatment.

At the screening visit, informed consent will be obtained before any trial-related assessments or procedures are performed. Initiation of the Abilify MyCite treatment will commence at the baseline visit (Day 1) for the subjects who meet all applicable eligibility criteria (Section 3.4), based on a series of assessments conducted at the screening visit. The first dose of Abilify MyCite is to be taken at the baseline (Day 1) visit (in the clinic) during onboarding, unless they have already taken their daily dose. Subjects should not take their oral standard-of-care medication that morning before the baseline visit.

During screening visit, the investigator will provide training on the correct use and required procedures associated with Abilify MyCite. The subject will be provided with patches, aripiprazole tablet embedded with an IEM sensor (Abilify MyCite) product, other supplies, and instructions on the procedures to be followed over the coming weeks.

Subjects will be monitored on the technology by the investigators, who can review the physician dashboard data and make changes to current treatment plan and therapy at their discretion. The investigators may request that a subject return to the site for unscheduled visits as deemed appropriate. In the event of an unscheduled visit, data collected will be at the investigator discretion per allowed data collection points noted in the schedule of assessments (Table 3.7-1). By Day 14 of the trial, if it is the opinion of the investigator that it is not appropriate for a subject to continue using Abilify MyCite, then the subject may be discontinued from trial participation but will be followed on oral atypical antipsychotic medication through the Month 6/ET visit.

Subjects will also visit the clinic for dispensing patches, Abilify MyCite product, and other supplies at Months 1, 2, 4, and 5. Any treatment changes, including reason for the change, will be recorded in the eCRF. Additionally, clinical evaluations will occur at Month 3 visit.

At the Month 6/ET visit, designated assessments and procedures will be conducted. The Month 6/ET visit marks the end of the assessment period. The subject will stop taking

Protocol 031-201-00301

Abilify MyCite product and will restart his/her standard-of-care treatment (routine follow-up from care teams). All trial materials will be returned to the trial site.

For subjects continuing on Abilify MyCite, a follow-up telephone contact will be made 30 days (\pm 3 days) after the last dose of aripiprazole tablet embedded with an IEM sensor (Abilify MyCite) product (for subjects who withdraw early and for those who complete the trial). The Month 6/ET visit will serve as the final safety visit for subjects who complete the study on standard-of-care treatment.

Trial assessment time points are summarized in [Table 3.7-1](#).

Protocol 031-201-00301

Table 3.7-1 Schedule of Assessments										
Assessments	Screening Days -45 to -1	Prospective Phase (Day 1 to Month 6/ET)^a							Follow -Up^b	Notes
		Abilify MyCite treatment required (Months 1 to 3)			Abilify MyCite or PRN oral atypical antipsychotic treatment (Months 4 to 6)					
		Baseline	Month 1	Month 2	Month 3	Month 4	Month 5	Month 6/ET	Month 7	
		Day 1	- 3/+ 2 days			- 3/+ 2 days			± 3 days	
Record retrospective hospitalization and intervention data per protocol	X ^c									
Informed consent	X									Section 3.4.1
Inclusion/exclusion criteria	X									Section 3.4
Demographic information	X									
Psychiatric history	X									
Urine pregnancy test (WOCBP) ^d	X	X								Section 3.7.3.2
Confirmation of diagnosis of schizophrenia by DSM-5	X									
C-SSRS (Baseline/Screening Version)	X									Section 3.7.3.5
C-SSRS (Since Last Visit Version)		X			X			X		Section 3.7.3.5
ECG collection	X									Section 3.7.3.4
Vital signs	X	X			X			X		Section 3.7.3.3
Adverse events	X	X			X			X	X	Section 5
Discontinue prohibited medications	X									Section 4
Smartphone verification	X									
Onsite onboarding with Abilify MyCite; subject pairs/applies patch		X								Section 3.2.2.2
Dispense aripiprazole tablet embedded with an IEM sensor (Abilify MyCite), patches, and other supplies		X	X	X	X	X ^e	X ^e			
Review Abilify MyCite dashboard data every 2 weeks		X	--X ^f --			--X ^f --			--X ^f --	

Protocol 031-201-00301

Table 3.7-1 Schedule of Assessments										
Assessments	Screening	Prospective Phase (Day 1 to Month 6/ET)^a							Follow-Up^b	Notes
		Baseline	Abilify MyCite treatment required (Months 1 to 3)			Abilify MyCite or PRN oral atypical antipsychotic treatment (Months 4 to 6)				
		Month 1	Month 2	Month 3	Month 4	Month 5	Month 6/ET	Month 7		
		Day 1	- 3/ + 2 days			- 3/ + 2 days			± 3 days	
Accountability for aripiprazole tablet embedded with an IEM sensor (Abilify MyCite), patches, and other supplies			X	X	X	X ^e	X ^e	X ^e		
Healthcare utilization record evaluation					X			X		Section 3.7.1.4
Subject usability and satisfaction scale					X			X ^g		Section 3.7.2.1.8
Follow-up phone call									X	

Protocol 031-201-00301

- ^a Monthly assessments will follow a 28-day schedule.
- ^b A follow-up phone call for subjects who conclude the study on Abilify MyCite will occur 30 days (\pm 3 days) after the Month 6/ET visit.
- ^c Retrospective hospitalization and intervention data will be collected only after trial eligibility is confirmed. This includes all psychiatric interventions (ie, hospitalizations, emergency department visits, partial hospitalization visits, intensive outpatient visits, assertive community treatment visits, outpatient visits for psychotherapy and/or medication management, etc.).
- ^d Urine pregnancy tests may be repeated if the investigator suspects that a subject is pregnant.
- ^e Abilify MyCite components (aripiprazole tablet embedded with an IEM sensor [Abilify MyCite], patches, and other supplies) will be dispensed and accountability performed only if subjects remain on Abilify MyCite treatment during Months 4 to 6 of the prospective phase. Any treatment changes, including reason for the change, will be recorded in the eCRF.
- ^f The trial physician is expected to regularly review the Abilify MyCite dashboard data during active Abilify MyCite use as consistent with routine care, approximately every 2 weeks. Note that "--x--" indicates an activity that occurs multiple times during the period.
- ^g Scales will be administered at the Month 6/ET visit for subjects who used Abilify MyCite during Months 4 to 6.

█

Protocol 031-201-00301

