
Trial Assessments:
	
Acceptance and Performance:
 
• Using feedback from subjects, investigators, and caregivers/support person on the use of Abilify MyCite:
• [REDACTED]• [REDACTED]• [REDACTED]• [REDACTED] 
[REDACTED]
 
[REDACTED]
 
[REDACTED]
 
[REDACTED]
 
[REDACTED]
 
[REDACTED]
 
[REDACTED]
 
[REDACTED]
 
[REDACTED]
 
Safety: Safety will be assessed by SAEs, device-related nonserious AEs, potential hepatotoxicity cases, pregnancies, product quality complaints, and suicidality assessment.

Criteria for Evaluation:
	
Primary Endpoint:
 
The primary endpoint is the comparison of inpatient psychiatric hospitalization rates (proportion of subjects with ≥ 1 inpatient psychiatric hospitalization) between the retrospective period (Months 1 to 3) while subjects are on oral standard-of-care antipsychotic treatment and the prospective period (Months 1 to 3) after the subjects switch to Abilify MyCite.
 
Secondary Endpoint:
 
• Improved adherence based on overall PDC with Abilify MyCite versus retrospective oral atypical antipsychotics.

Protocol 031-201-00301

Exploratory Endpoints:

- █ [REDACTED]
- █ [REDACTED]

[REDACTED]

- █ [REDACTED]
- █ [REDACTED]
- █ [REDACTED]
- █ [REDACTED]
- █ [REDACTED]
- █ [REDACTED]
- █ [REDACTED]
- █ [REDACTED]
- █ [REDACTED]
- █ [REDACTED]
- █ [REDACTED]
- █ [REDACTED]
- █ [REDACTED]
- █ [REDACTED]
- █ [REDACTED]

Protocol 031-201-00301

	
Safety Endpoints:
 
Adverse events will be examined by frequency, severity, seriousness, and discontinuation (all cause and due to AEs). The safety and tolerability of Abilify MyCite, as assessed by the frequency and severity of SAEs, device-related nonserious AEs, potential hepatotoxicity cases, and pregnancies will be assessed along with an evaluation of any product quality complaints that arise. The Columbia Suicide Severity Rating Scale (C-SSRS) will be completed at baseline and all subsequent visits to assess the risk of suicide events and to classify reported suicide events.

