3.7.1.3.5 Month 6/Early Termination Visit

Month 6/ET (- 3/ + 2 days) will be an investigator visit for the subject. In addition, Month 6/ET visit evaluations are to be completed for any subject withdrawn from the trial at any time (for any reason other than full withdrawal of the consent). At the Month 6/ET visit, the following will be performed:

- Administer the suicidality assessment (C-SSRS Since Last Visit Version; [Section 3.7.3.5](#)).
- Perform vital signs assessment ([Section 3.7.3.3](#)).
- Monitor AEs, including device-related nonserious AEs ([Section 5](#)).
- Accountability of patches and Abilify MyCite product (aripiprazole tablet embedded with an IEM sensor) supplies performed for subjects remaining on Abilify MyCite treatment. Any treatment changes, including reason for the change, will be recorded in the eCRF.
- Review Abilify MyCite dashboard data every 2 weeks for subjects remaining on Abilify MyCite treatment.

Protocol 031-201-00301

- [REDACTED]
- [REDACTED]
- [REDACTED]
- [REDACTED]
- [REDACTED]
- [REDACTED]
- Healthcare utilization record evaluation ([Section 3.7.1.4](#)).
- [REDACTED]
- [REDACTED]
- [REDACTED]
- [REDACTED]

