3.8.3 Individual Subject Discontinuation

3.8.3.1 Treatment Discontinuation

After enrollment, a subject may stop Abilify MyCite treatment permanently for a variety of reasons. Treatment discontinuations may be initiated by a subject who is not satisfied with treatment or may become medically necessary due to AEs, device-related nonserious AEs, required treatment with a disallowed medication or therapy, or other issues, as determined by the investigator. For subjects who elect to discontinue early for any reason, the sponsor would like to follow the subject for the total trial duration to track healthcare utilization with and without use of Abilify MyCite.

By Day 14 of the trial, if it is the opinion of the investigator that it is not appropriate for a subject to continue using Abilify MyCite, then the subject may be discontinued from trial participation but will be followed on oral atypical antipsychotic medication through the Month 6/ET visit.

If any subject discontinues the trial early, every effort should be made to complete the Month 6/ET evaluations (see [Table 3.7-1](#)) at that visit. All subjects (completers and early withdrawals) will be contacted to monitor for safety events via telephone or investigator visit at 1 month (\pm 3 days) after the Month 6/ET visit.

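### Footnote g of Table 3.7-1 leaves a subject who exits before Month 3 with no scheduled usability and satisfaction rating, which conflicts with Section 3.7.1.3.5

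*Protocol*

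**What the plan says.** In the protocol's schedule of assessments (Table 3.7-1, Section 3.7), the row "Subject usability and satisfaction scale" is marked at two visits only: Month 3, with no footnote, and Month 6/ET, with footnote g. There is no mark at baseline, Month 1 or Month 2. Footnote g reads: "Scales will be administered at the Month 6/ET visit for subjects who used Abilify MyCite during Months 4 to 6".

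Two other places deal with early termination:

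- Section 3.7.1.3.5: "Month 6/ET visit evaluations are to be completed for any subject withdrawn from the trial at any time". The one exception is full withdrawal of consent.
- Section 3.8.3.1: if a subject leaves early, "every effort should be made to complete the Month 6/ET evaluations", with a cross-reference to Table 3.7-1.

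The synopsis lists acceptance and performance among the trial assessments: "Using feedback from subjects, investigators, and caregivers/support person on the use of Abilify MyCite". Section 3.8.3.1 states: "Treatment discontinuations may be initiated by a subject who is not satisfied with treatment". Section 1.3.1.1 lets investigators withdraw subjects whose skin changes at the patch site are unacceptable.

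Footnote e of the same table restricts another activity in similar terms. Supplies "will be dispensed and accountability performed only if subjects remain on Abilify MyCite treatment during Months 4 to 6".

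**The concern.** Footnote g has an evident purpose. A subject moved to standard of care at Month 3 has just rated the system and need not rate it again at Month 6. But the wording also takes in a different group: subjects whose early termination visit falls before Month 3. They did not use the product in Months 4 to 6, and they have not yet been asked. A site that follows the footnote omits the scale at that visit; a site that follows Section 3.7.1.3.5 gives it.

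The loss is unlikely to be random with respect to opinion, because the protocol itself names dissatisfaction and skin reactions as grounds for stopping or withdrawal. An acceptance summary drawn from subjects still present at Month 3 would tend to miss the less favourable views. Those views matter for the sponsor's stated aim, in Section 1.3.2, of using trial feedback to refine the app. A rating not taken at exit may not be recoverable later.

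**Working it through.** **Who is scheduled for the scale, reading Table 3.7-1 alone**

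| Course of the subject | Month 3 scale | Month 6/ET scale under footnote g |
|---|---|---|
| Stays on MyCite to Month 6 | Yes | Yes |
| Switches to standard of care at Month 3 | Yes | No, but already asked once |
| Stops MyCite before Month 3, stays in follow-up | Yes | No, but already asked once |
| Leaves the trial before Month 3 | No | No |

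Only the last row has no rating. Under Section 3.7.1.3.5 that row would read yes at ET unless consent was fully withdrawn. Section 3.8.3.1 does not settle the matter, because it points back to the same table.

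**How many subjects could be affected**

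Inputs: about 320 enrolled and 224 to complete (Section 3.3). Section 7.1 ties the 224 to completing the 3-month treatment.

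- Reproducing the plan's figure: 224 / (1 − 0.30) = 320. The 30% is implied by the two numbers; it is not stated.
- Non-completers: 320 − 224 = 96, and 96 / 320 = 30%.

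This is a ceiling. The 96 include subjects lost to follow-up and subjects who withdraw consent, whom no rewording would reach. They also include subjects who stop MyCite but remain to Month 3, who are asked there. In addition, Section 3.10 defines treatment completers by the Month 6/ET visit; on that definition some of the 96 could leave after Month 3, having already answered.

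**Size of the bias**

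Let m be the share not asked, p the acceptance among those asked and q the acceptance among those not asked, taking the 320 as the number dosed. The reported figure is p. The figure over all dosed subjects is (1 − m)p + mq. The difference is

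overstatement = m × (p − q).

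Neither p nor q is in the documents. The values below are assumptions that show the range.

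| m | p | q | Overstatement |
|---|---|---|---|
| 30% | 80% | 80% | 0.30 × 0 = 0 points |
| 30% | 80% | 50% | 0.30 × 0.30 = 9 points |
| 30% | 80% | 40% | 0.30 × 0.40 = 12 points |
| 30% | 80% | 0% | 0.30 × 0.80 = 24 points |
| 10% | 80% | 40% | 0.10 × 0.40 = 4 points |
| 30% | 80% | 100% | 0.30 × (−0.20) = −6 points |

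The last row shows that the sign reverses if those not asked are the more satisfied group.

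**The case against.** The strongest answer is that footnote g does not contain the word only, whereas footnote e does. It can be read as dealing just with subjects who reach Month 6, leaving early terminators to the general rule in Section 3.7.1.3.5. On that reading they are asked. A reader might infer from footnote g that everyone who leaves early is never asked; the documents do not support that. They support a conflict between a specific footnote and a general rule, which a site would have to resolve for itself.

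Second, stopping treatment is not leaving the trial. The sentence on dissatisfaction concerns treatment. The same section says the sponsor would like to follow those who stop early for the whole trial, and subjects taken off MyCite by Day 14 "will be followed on oral atypical antipsychotic medication through the Month 6/ET visit". A dissatisfied subject who stays in follow-up reaches the unrestricted Month 3 scale. This stands, and it narrows the affected group.

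Third, Section 3.7.2.1.8, which describes the scale, is redacted, as are several visit bullets and much of the exploratory analysis text. The scale's own rules and its analysis population cannot be seen. This also stands, and it is why overstatement is likely but not shown.

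A reader might also infer from footnote e that drug intake is unknown for early leavers. That does not follow. Section 3.2.2.3 has every subject return all supplies, and Section 8.3 requires an inventory of product dispensed, administered and returned, without condition. Section 3.7.1.3.5 performs accountability at ET for subjects still on MyCite, with no Months 4 to 6 limit. The system also time-stamps ingestions. Only the footnote's wording is out of line.

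**Conclusion.** The point holds as a minor one. As written, footnote g gives no scheduled rating to a subject who leaves before Month 3, and this conflicts with Section 3.7.1.3.5. Acceptance is likely to be overstated if early leavers are less satisfied than those who stay. That direction is plausible from the protocol's own list of reasons for stopping and withdrawal, but it is not demonstrated. At most 96 of 320 subjects (30%) are involved. The bias is m × (p − q); any figure in points rests on assumed acceptance rates.

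The scale is neither the primary nor the secondary endpoint, and nothing here is shown to affect hospitalization or the proportion of days covered. On accountability, what remains is a wording mismatch between footnote e and the body of the protocol.

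**What to change.** 1. Reword footnote g: at Month 6/ET the scale goes to every subject who has used Abilify MyCite since the scale was last given, or since Day 1 if it has not yet been given. State that this includes early terminations before Month 3. Subjects who switch at Month 3 are still spared a repeat.
2. Summarise the scale with and without the ET ratings of early terminators, and report the number asked out of all dosed subjects.
3. Align footnote e, as it applies to accountability at ET, with Sections 3.7.1.3.5, 3.2.2.3 and 8.3.

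The cost is two footnotes, an added summary and one short questionnaire at a visit that is already required. The reported acceptance figure may come out less favourable. Subjects who are lost or who fully withdraw consent will still be missing, which is why the count in item 2 is needed.

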3.7.1 Schedule of Assessments

3.7.1.1 Retrospective Phase (6 Months)

Subjects must have been prescribed oral antipsychotic standard-of-care pharmacotherapy for at least 6 months or longer, with evidence of prescription (ie, pharmacy records), during the retrospective phase and prior to screening. Subjects administered antipsychotics other than aripiprazole may cross-titrate onto oral aripiprazole during the screening period at the discretion of the investigator to be eligible for trial participation.

All hospitalizations and all interventions (psychiatric only) will be recorded in the source documentation.

3.7.1.2 Screening Visit

Eligible subjects will come to the trial site, on a day agreed upon by the subject (and his or her caregiver/support person, if applicable) and the investigator, to undergo screening assessments.

At the screening visit, the following will be performed:

- Retrospective hospitalization and intervention data will be collected only after trial eligibility is confirmed.
- Informed consent ([Section 3.4.1](#)).
 - The subject must provide documented informed consent before any other trial assessments or procedures are performed.
 - If the subject has a caregiver/support person, that caregiver/support person also must provide written informed consent.
- Eligibility Assessment ([Section 3.4](#)).
 - All protocol inclusion and exclusion criteria will be reviewed by the investigator; only subjects who meet all of the inclusion criteria and none of exclusion criteria may be considered for further participation in the trial.
- Obtain demographic information and psychiatric history.
- Obtain urine sample for pregnancy test (women of childbearing potential [[WOCBP](#)]; [Section 3.7.3.2](#)).
- Confirm diagnosis of schizophrenia by DSM-5.
- Administer the suicidality assessment (C-SSRS baseline version; [Section 3.7.3.5](#)).
- Perform electrocardiogram (ECG) collection ([Section 3.7.3.4](#)).
- Perform vital signs assessment ([Section 3.7.3.3](#)).
- Monitor AEs, including device-related nonserious AEs ([Section 5](#)).
- Discontinue prohibited medications ([Section 4](#)).

Protocol 031-201-00301

- Smartphone verification: Each subject will be asked to confirm the availability of a suitable smartphone for the trial, in addition to confirming a wireless local area networking (wireless fidelity [Wi-Fi]) connectivity option is available to them. A subject with a smartphone that is not compatible with the Abilify MyCite app will be offered a loaner phone for the trial period.
- [REDACTED] (Section 3.7.2.1.2).

